### 10.1 Follow-up Visit Windows

Follow-up assessments will be done at:

Day 0 = day of procedure	Type of follow-up
30 days – 7 days/+ 14 days	Clinic Visit
6 mo ± 30 days	Clinic visit
12 mo ± 30 days	Clinic visit
24 & 36 mo ± 30 days	Clinic visit

The date for the 30-day follow-up should be calculated by adding 30 days to the index procedure date (e.g. treatment on December 5th, 30 day follow up on January 4th). The dates for the 6-, 12-, 24-, and 36 months follow-up assessments should be calculated using the anniversary date of the index procedure (e.g. procedure on December 5th, 6-month follow up on June 5th, 12 month and annual thereafter on December 5th). If the procedure was performed on the 31st and the follow-up month has only 30 days, the anniversary should be calculated to the first day of the next month. Visit window calculations will be provided for each subject through the EDC system.

## 10.2 General Analysis Definitions

Assessments will be presented chronologically by study day, which is defined in the following:

Study day = assessment day – date of index-procedure.

Index-procedure day = 0. Events occurring on the day of the index-procedure will be considered day 0.

Note: if the staged procedure is 14 days post index-procedure and an event occurs on this day this event will be reported on day 14 even if it is clearly attributed to the staged procedure.

Events occurring on the day of discharge will be considered in-hospital.

Time of follow-up = date of last contact – date of index procedure. where date of last contact includes but not limited to date of death or the latest of: (1) date of last adverse event, (2) date of last image, (3) date of last procedure, (4) date of last scheduled or unscheduled -follow-up visit, (5) date of Study Exit.

Events will be reported up to the number of months times 30. So, for 6 months  $6 \times 30 = 180$  days will be used, and for 12 months or 1 year, 360 days will be used. For analysis at each time point, subjects will be censored at the time point or time to follow-up as defined above, whichever is earlier.

For all the clinical/safety endpoints, the denominator will include subjects who either have an adjudicated event (e.g. death, revascularization) before the time of interest, or have a contact beyond the lower window of the follow-up.

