### 10.14.2 Lost-to-Follow-up

The subject may only be considered lost to follow-up after all efforts to obtain compliance are exhausted. At a minimum, four attempts must be made to contact the subject and documented in the subject's records:

- 3 telephone attempts to the subject's last known phone number, and if unsuccessful,
- 1 certified letter from the PI to the subject's last known address

If the site is unable to reach the subject after the documented attempts, the site should make every attempt to verify the subject's vital status (alive or deceased). A Study Exit eCRF should be completed. If the subject returns to the study site thereafter, the Study Exit eCRF can be deleted and follow-up data can be collected. A Deviation eCRF should be completed for the missed visit(s), if appropriate.

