### 10.3.1 Clinical/Safety Endpoints

Clinical/safety endpoints include repeat revascularization procedure on target lesions/vessels and safety endpoints including MAEs (composite and individual components). Most of the event rates of the clinical/safety endpoints will be calculated on patient basis and for different reporting time points, the corresponding cutoff days will be used: 30 days for 30-day; 180 days for 6-month; 360 days for 12-month; 720 days for 24-month; and 1080 days for 36-month.

For each visit (or reporting time point), the event rate will be calculated as the proportion of number of subjects with certain event term over the number of evaluable subjects, the denominator of the event rate calculation will be event specific. The evaluable subjects at each reporting time point include all subjects who are included by the snapshot date and

- 1) Had an event within (on or before) the reporting cutoff days, or
- 2) Had a follow-up at or after the lower limit of the reporting window, or
- 3) The withdrawal consent date/recorded lost-to-follow-up date at or after the lower limit of the reporting window

'Days to event' (date of earliest event – date of index procedure) and 'Days to last contact' (date of last contact – date of index procedure) are usually used for the determination of the eligibility of the 'evaluable subject'. The last contact date will be calculated based on the information gathered from all available dates during the follow-ups.

The 'Reporting Cutoff Days', 'Lower limit of the Reporting Window' and the correspondent visits are as the following:

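### For subjects lost to follow-up, SAP 10.2 counts an undefined Study Exit date as contact; if that date is administrative, event-free Kaplan-Meier estimates can only stay the same or rise

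*SAP*

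**What the plan says.** SAP 10.2 defines time of follow-up from the date of last contact, "where date of last contact includes but not limited to date of death or the latest of" five listed dates: last adverse event, last image, last procedure, and then "4) date of last scheduled or unscheduled -follow-up visit, (5) date of Study Exit". At each time point "subjects will be censored at the time point or time to follow-up as defined above, whichever is earlier". Because the rule takes the latest date, Study Exit overrides an earlier visit, image or procedure.

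Protocol 10.14.2 governs subjects lost to follow-up: "At a minimum, four attempts must be made to contact the subject". If these fail, the site tries to verify the subject's "vital status (alive or deceased). A Study Exit eCRF should be completed". The date to enter on that form is not specified. Protocol 10.14.1 does tie the form to the last point of contact, but in the section on withdrawals.

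SAP 10.3.1 sets the denominators for proportions. One route to being evaluable is "Had a follow-up at or after the lower limit of the reporting window"; a separate route is "The withdrawal consent date/recorded lost-to-follow-up date at or after the lower limit of the reporting window". SAP 10.2 puts the denominator rule differently: subjects need an adjudicated event "or have a contact beyond the lower window of the follow-up".

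Three sets of Kaplan-Meier analyses are concerned. SAP 7.9.1.2 censors the supportive 12-month patency analysis by the Appendix A definition. SAP 7.9.3 plans MAE analyses to 36 months, covered by the general rule in 10.2. Protocol 14.4.2 censors 36-month freedom from TLR at a last contact date that it does not define; SAP v4.0 (February 2020) predates that endpoint, which came with CIP v2.0 (March 2021).

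**The concern.** A subject should count in the risk set only while an event would be seen if it happened. For a lost subject, the Study Exit form follows a series of failed contacts, so the day it is completed necessarily falls after the last real contact. If that day is the date recorded, the interval in between counts as event-free time although nobody was observing.

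The separate lost-to-follow-up route in SAP 10.3.1 suggests that this recorded date can differ from the last follow-up, since otherwise it would add little. It does not prove it.

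At stake are the reported long-term rates and their intervals. For freedom from TLR, the primary endpoint of the post-approval phase, the Kaplan-Meier estimate and its interval are the whole result.

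**Working it through.** The plan gives no figure on this point to reproduce, so the check is of direction and then of size.

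**Direction.** The Kaplan-Meier estimate is S(t) = Π(1 − d_i/n_i). Moving an event-free subject's censoring date later leaves every d_i unchanged and can only keep or raise each n_i. Each factor, and so S(t), is equal or higher. Shown as a cumulative event rate, the result is equal or lower. In a separate simulation of 200-subject trials, the difference was never negative.

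**Inputs.** The documents give no 36-month loss or TLR figure, so these are assumptions:
- Lost: 3.5% to 20%, the planning allowances for the 30-day and 12-month endpoints (protocol 5.2), used only as range ends.
- 36-month TLR: 8.3% (the literature 12-month rate, protocol 5.1.1, as a floor) to 1 − (1 − 0.083)³ = 22.9%; 15% as a middle value.
- Constant hazard; visits at days 0, 30, 180, 360, 720 and 1080; non-informative loss, uniform over 0-1080 or late (720-1080); every lost subject carries an administrative date.

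**Hand check: late loss, 20% lost, 15% TLR.** The last visit is day 720. An exit 30 days after the missed 36-month visit is day 1110, so these subjects count as event-free to day 1080. If later TLRs are not learned of, the estimate tends to 0.8 × S(1080) + 0.2 × S(720). With S(1080) = 0.85 and S(720) = 0.85^(720/1080) = 0.8973, the rise is 0.2 × (0.8973 − 0.85) = 0.0095, or +0.95 points.

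**Bias in 36-month freedom from TLR, in points, 20% lost, uniform loss** (large-sample limit by numerical integration):

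| Censoring date for lost subjects | TLR 8.3% | 15% | 22.9% |
|---|---|---|---|
| *(a) TLRs after the last visit never learned of* | | | |
| Last visit | 0.00 | 0.00 | 0.00 |
| Exit 75 days after last visit | +0.12 | +0.21 | +0.30 |
| Exit 30 days after next missed visit | +0.51 | +0.89 | +1.32 |
| All exits at or after day 1080 | +1.04 | +1.86 | +2.80 |
| *(b) TLRs captured up to true loss* | | | |
| Last visit | −0.25 | −0.43 | −0.62 |
| Exit 75 days after last visit | −0.13 | −0.22 | −0.31 |
| Exit 30 days after next missed visit | +0.27 | +0.47 | +0.69 |

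The rise caused by the rule is an exit row minus the last-visit row. The largest rise with exit after the missed visit comes from late loss under (b) at 22.9% TLR: 0.69 − (−0.81) = 1.50. At 3.5% lost under (a) with the same exit rule and uniform loss, the rise is 0.08 to 0.21. If only half the lost subjects carry an administrative date (10% lost, 15% TLR, exit after the missed visit), the bias is +0.22 under (a) and +0.02 under (b).

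**Interval width.** 20% lost, 15% TLR, capture (a), n = 200. Peto SE = S√[(1 − S)/n_t], with n_t the number at risk at day 1080.
- Last visit: n_t = 200 × 0.8 × 0.85 = 136; 0.85 × √(0.15/136) = 2.82 points.
- Study Exit, uniform loss: n_t = 148; 0.8589 × √(0.1411/148) = 2.65.
- Study Exit, late loss: n_t = 136 + 40 × 0.8973 = 172; 0.8595 × √(0.1405/172) = 2.46.

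The SE is thus 6-13% smaller.

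**Other placement of losses.** The separate simulation put losses on visit days (30, 180, 360, 720), with 20% lost and 22.9% TLR. Exit 60, 180 or 365 days later, or at the end of the horizon, raised the estimate by 0.2, 0.8, 1.5 and 3.1 points. The last value exceeds 2.8 because follow-up ends earlier on average. For 12-month patency at 85.7% and 20% lost, exit 60, 180 or at least 365 days later gave +0.5, +1.4 and +2.0.

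**The case against.** The strongest objection is that the premise cannot be seen. The form is not in the documents. Protocol 10.14.1 links it to the last point of contact, SAP 10.3.1 says that last contact is worked out from all available dates during follow-up, and protocol 14.4.2, read plainly, already censors at contact. The two routes in SAP 10.3.1 need not be redundant either: the first may mean a study visit and the second a later contact without a visit, and both govern denominators rather than censoring. All of this stands as a limit on confidence. None of it says what is entered for a lost subject, and the latest-of rule has no safeguard if the date is administrative.

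A reader might also cite protocol 10.10, which tells sites not to exit a subject at once after a 36-month phone encounter. That is weak support: the subject has been reached, and between day 1050, when the visit window opens, and day 1080, when the analysis stops, at most 30 days are added.

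A third objection is that last-contact censoring is not always less biased. Revascularizations of the target limb remain reportable (protocol 12.2.4), so capture after the last visit is plausible. Under (b) with a 75-day delay, the existing rule is closer to the truth (−0.22 against −0.43 at 15% TLR and 20% lost). This stands, and it means that the two versions do not always bracket the truth: here both are low.

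Finally, the 36-month figures are for TLR. The only composite MAE rate in the documents is 5.6% within 30 days, so a constant 36-month hazard does not carry over to MAE.

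**Conclusion.** The concern holds in conditional form and is minor. The SAP states a rule that can keep unobserved subjects at risk, and the documents leave open whether it does. If it does, event-free estimates are equal or higher, and intervals narrower, for the 12-month patency and MAE analyses directly and for 36-month freedom from TLR by inference.

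Under the stated assumptions, with every lost subject carrying an administrative date, the 36-month estimate rises by 0-0.3 points (exit 75 days after the last visit), 0.1-1.5 (exit 30 days after the next missed visit), and about 2.8 in the bounding case. That is usually less than one SE. The MAE effect is not quantified.

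Two stronger readings are tempting. One is that the plan does inflate its long-term results; the documents do not support this, because the recorded date is unknown. The other is that study success is affected. It is not: the pivotal tests are proportions of evaluable subjects (protocol 14.4.1), not Kaplan-Meier estimates, and the post-approval phase has no success criterion (protocol 14.5). Study Exit also remains a valid contact for completers and for withdrawals made in conversation.

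**What to change.** In SAP 10.2, for subjects lost to follow-up, do not count the Study Exit or lost-to-follow-up date as a contact unless the exit was itself a contact. Censor at the latest date on which event status was ascertained: visit, phone encounter, image, procedure, reported event or withdrawal conversation. State which date the Study Exit form carries for a lost subject, and refer protocol 14.4.2 to the same definition.

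Make the third route in SAP 10.3.1 consistent with this, but do not simply delete it. Deletion drops lost subjects' non-events and keeps their events: at 15% TLR, 20% lost uniformly, capture (a), the bias in the simple proportion free of TLR goes from about −0.1 to about −1.2 points.

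Report how many subjects have a last contact set only by Study Exit, and show the Study Exit version as a sensitivity analysis, without claiming that the two versions bracket the truth.

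The cost is edits to three sections, one re-derived date, one count and one extra run. Whether existing form fields separate last contact from exit needs checking. The estimate will be equal or slightly lower and the interval slightly wider. If TLRs between the last visit and true loss are captured, the new estimate is low by about 0.2-0.6 points (10-20% lost, 15% TLR). If the form already carries the last real contact, one sentence saying so closes the point.

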## 10.3 Specific Reporting Conventions

Three types of endpoints will be reported – Clinical/safety endpoints, Imaging endpoints, and endpoints assessed by clinic visit. The reported windows are specified for each type of the endpoints below.

### 10.3.1 Clinical/Safety Endpoints

Clinical/safety endpoints include repeat revascularization procedure on target lesions/vessels and safety endpoints including MAEs (composite and individual components). Most of the event rates of the clinical/safety endpoints will be calculated on patient basis and for different reporting time points, the corresponding cutoff days will be used: 30 days for 30-day; 180 days for 6-month; 360 days for 12-month; 720 days for 24-month; and 1080 days for 36-month.

For each visit (or reporting time point), the event rate will be calculated as the proportion of number of subjects with certain event term over the number of evaluable subjects, the denominator of the event rate calculation will be event specific. The evaluable subjects at each reporting time point include all subjects who are included by the snapshot date and

- 1) Had an event within (on or before) the reporting cutoff days, or
- 2) Had a follow-up at or after the lower limit of the reporting window, or
- 3) The withdrawal consent date/recorded lost-to-follow-up date at or after the lower limit of the reporting window

'Days to event' (date of earliest event – date of index procedure) and 'Days to last contact' (date of last contact – date of index procedure) are usually used for the determination of the eligibility of the 'evaluable subject'. The last contact date will be calculated based on the information gathered from all available dates during the follow-ups.

The 'Reporting Cutoff Days', 'Lower limit of the Reporting Window' and the correspondent visits are as the following:

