## 10.10 24 and 36 Months ( $\pm$ 30 days) Post-Procedure Follow-Up Assessment

Subjects will be seen in the office at 24 months (690-750 days) and 36 months (1050-1110 days) post-procedure. The following evaluations will be completed and data recorded on the Follow-up eCRF:

- Physical assessment of limbs;
- Villalta Score and VCSS (both limbs);
- Quality of Life Questionnaires: EQ-5D and VEINES-QOL/Sym;
- INR for subjects on warfarin;
- Duplex Ultrasound (target limb);
- Duplex ultrasound (contralateral limb); image of the CFV waveform only.
- X-ray (target limb);
- Adverse events/device deficiency;
- Medications: Antithrombotics, Antibiotics, Immunosuppressants, NSAIDs, Steroids, Diuretics, Calcium-channel blockers, Statins;
- Discontinuation information (in case the subject ends involvement in the study).

In the event that an in-clinic 24 and/or 36 Month visit is unable to be performed (i.e. Missed Visit) a 'Phone Encounter' may be completed. The purpose of the 'Phone Encounter' is to capture subject status including the following:

- Date of contact (phone encounter)
- Medications: Antithrombotics, Antibiotics, Immunosuppressants, NSAIDs, Steroids, Diuretics, Calcium-channel blockers, Statins;
- Adverse events/device deficiency;

The 'Phone Encounter' does not replace the 24- and/or 36-month visit. If a 'Phone Encounter' is completed for the 36-month visit, the subject should not be immediately exited from the study. The site should continue to attempt to schedule an in-clinic visit as specified above when it is appropriate to do so and work with Medtronic to understand how long the study will remain open.

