### **10.12.6.4 X-ray**

During the following timepoints an X-ray (target limb) is required to assess stent fracture:

- at 30-days for first safety analysis for the first 30 subjects;
- at 12, 24, and 36 months for all subjects;
- during reinterventions (unscheduled visits) pre- and post- reintervention.

All X-ray examinations should be performed according to the core laboratory guidelines and are analyzed by an independent core laboratory (See **Section 13.4**).

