## 1. Version History

Version	Summary of Changes	Author(s)/Title
1.0, 12/DEC/2016	
 
New Document
 
	[name], Prin Statistician
2.0, 12/JUL/2017	
 
PMA will be submitted to FDA when all 12-month follow-up data are available. All references to "PMA will be submitted to FDA when the evaluable data are available". Applicable sections are 7.1.3 and 7.6.1.
 
Time-to-event analyses for primary patency and MAE through 12-month are added. Applicable sections are 7.3.2. and 7.8.
 
Race/Ethnicity covariates are added for center pooling and multiple imputation. Application sections are 7.5 and 7.6.1.
 
Patients inclusion restriction is added in section 6.3.
 
	[name], Prin Statistician
3.0, 13/DEC/2019	
 
Updated the SAP template using 056-F286 vA
 
Updated SAP content per CIP V1.4
 
Updated covariates list for center pooling and multiple imputation 7.3 and 7.4.1
 
Added analysis method for secondary endpoints 7.9.3 Updated primary patency composite endpoint determination rule 10.3.2.2
 
Clarified thrombosis and stent migration, confirmed by core lab imaging, are treated as clinical/safety events; the algorithm for thrombosis and stent migration updated
 
Added primary assisted patency and secondary patency algorithms 10.3.2.3
 
Added analysis window for unscheduled clinic visit 10.3.3
 
	[name], Prin Statistician
4.0, 14/FEB/2020	
 
Correction of Version date for Version 3 in Summary of Changes Table. There is no content change.
 
	[name], Prin Statistician

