## 7.9.2 Primary Safety Endpoint

The primary safety endpoint of this study will be the incidence of composite Major Adverse Events (MAE) at 30 days following stenting of an obstruction in the iliofemoral venous segment. MAEs will be adjudicated by a Clinical Events Committee (CEC), except for stent thrombosis and stent migration as they are confirmed by core laboratory.

The components of the 30-day MAE composite include:

- All-cause death occurring post-procedure
- Clinically significant (i.e. symptomatic, confirmed by CT pulmonary angiography) pulmonary embolism
- Major bleeding complication (procedural)
- Stent thrombosis confirmed by imaging as assessed by core laboratory
- Stent migration confirmed by imaging as assessed by core laboratory

Note: Migration excludes stent dislodgement at the index procedure as may occur with under-sizing of a stent.

More details of the reporting rules are used to determine this endpoint can be found in section 10.3.1.

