**Late success secondary endpoints**

- 4. Primary Assisted Patency at 12 months:** Uninterrupted patency of the stented segment of the target lesion with a secondary intervention, also known as an adjunctive treatment (e.g. balloon venoplasty, subsequent stenting, etc.).
- 5. Secondary Patency at 12 months:** Patency of the stented segment of the target lesion after subsequent intervention for an occlusion.
- 6. Target Lesion Revascularization (TLR) through 30 days, 6-, 12-, 24- and 36 months:** Any reintervention of the stented segment of the target lesion.
- 7. Major Adverse Events (MAE) through 6-, 12-, 24- and 36 months:** MAEs include:
  - All-cause death occurring post-procedure
  - Clinically significant (i.e. symptomatic, confirmed by CT pulmonary angiography) pulmonary embolism
  - Major bleeding complication (post-procedural)
  - Stent thrombosis confirmed by imaging as assessed by core laboratory
  - Stent migration confirmed by imaging as assessed by core laboratoryNote: Migration excludes stent dislodgement at the index procedure as may occur with undersizing of a stent  
All MAEs will be adjudicated by a CEC, except for stent thrombosis and stent migration as they are confirmed by core laboratory.
- 8. Delayed Stent Migration at 12-, 24-, and 36 months:** position change of a venous stent observed with an imaging modality > 1 cm from its original location at the conclusion of the index procedure, as determined with regard to a reference anatomic structure.
- 9. Stent Fracture at 30 days, 12-, 24- and 36 months:**  
Fracture or breakage of any portion of the stent.  
Determined by X-ray for the first 30 subjects at 30 days and for all subjects (including the first 30 subjects) at 12-, 24- and 36 months using the following classifications (36) as adjudicated by a venous stent fracture core laboratory:
  - i. Type 0 – No strut fractures
  - ii. Type I – Single tine fracture
  - iii. Type II – Multiple tine fractures
  - iv. Type III – Stent fracture(s) with preserved alignment of the components
  - v. Type IV – Stent fracture(s) with mal-alignment of the components
  - vi. Type V – Stent fracture(s) in a trans-axial spiral configuration
- 10. Change in VEINES-QOL/Sym Score at 6-, 12-, 24- and 36 months:** Defined as the change in VEINES-QOL/Sym score at 6, 12, 24, and 36 months compared to baseline.

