### 10.3.2.4 Stent Fracture/Delayed Stent Migration

These endpoints are reported by core laboratory imaging. The proportion rate of these endpoints will be constructed cumulatively on both stent level and subject level.

**Numerator:** subject/stent with any positive findings determined by scheduled visits and unscheduled image from day 0 to the upper limit of the imaging reporting window specified in Table 4.

**Denominator:** all *qualified* subjects/stents at a given visit – all subjects/stents with completed and evaluable imaging as part of the scheduled visit, or with unscheduled imaging within the imaging reporting window specified for that visit (all imaging data should be evaluable), plus subjects/stents with positive findings before that timepoint.

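### Late MAE rates: a subject with a contact but no image counts as observed and free of stent thrombosis and migration, so these two components can be understated

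*SAP*

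**What the plan says.** **Event definition.** In the 6- to 36-month MAE endpoint (SAP 7.9.3), thrombosis counts as "Stent thrombosis confirmed by imaging as assessed by core laboratory". Migration carries the same condition, in the wording also used in 7.9.2: "Stent migration confirmed by imaging as assessed by core laboratory". Protocol Appendix B adds that stent thrombosis may be diagnosed by duplex but needs venogram or IVUS confirmation.

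**Endpoint class.** The SAP version history records the choice for version 3.0: "Clarified thrombosis and stent migration, confirmed by core lab imaging, are treated as clinical/safety events".

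**Who is evaluable.** Under SAP 10.3.1 a subject is evaluable with an event by the cutoff, or "Had a follow-up at or after the lower limit of the reporting window", or on a third ground: "The withdrawal consent date/recorded lost-to-follow-up date at or after the lower limit of the reporting window". Table 2 sets the lower limits at day 150, 330, 690 and 1050. Last contact is built from every date available. SAP 10.2 gives an open-ended list that includes the last adverse event and study exit, and censors at the earlier of the time point and last contact. SAP 7.9.3 plans Kaplan-Meier estimates for MAE and its components through 12 months and annually to 36.

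**Imaging and contact schedule.** X-ray is required "at 12, 24, and 36 months for all subjects" (Protocol 10.12.6.4), and at 30 days in the first 30 subjects only. Duplex is done at every visit. A venogram is conditional at 12 months and discretionary at other follow-up visits without a re-intervention (Protocol 10.12.6.1). If a 24- or 36-month visit is missed, Protocol 10.10 allows a phone contact: "The purpose of the 'Phone Encounter' is to capture subject status". It records the contact date, medications and adverse events or device deficiencies.

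**The neighbouring rule.** For stent fracture and delayed stent migration, SAP 10.3.2.4 builds the denominator from "all subjects/stents with completed and evaluable imaging as part of the scheduled visit", or unscheduled imaging in the window, plus earlier positive findings.

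**The concern.** The numerator needs an image and the denominator does not. A subject reached only by telephone at 24 months is left out of the delayed-migration denominator but counted as free of MAE migration at the same time point. The third ground goes further: under Protocol 10.14.2 lost-to-follow-up status is assigned after contact attempts have failed, so a subject nobody could reach can be counted as observed and event-free.

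Unimaged subjects are foreseeable. Protocol 10.13 says COVID-19 began during the 24-month follow-up phase and gives declined visits and closed sites as examples of deviations. The post-approval phase is meant to describe long-term safety and has no hypothesis test, so these descriptive rates are an important part of its safety evidence.

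**Working it through.** **1. Does any rule require an image?** SAP 10.2, 10.3.1 and Table 2 do not. The event-specific denominators of Table 3 do not help either: that table covers 30 days and defines evaluability by days of clinical follow-up. The only imaging-based denominator for a stent-position endpoint is in 10.3.2.4, and it is not applied to the MAE components.

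**2. The plan's own figures.** The documents state no expected MAE rate for 6 to 36 months. The nearest stated figure is the 30-day safety design in SAP 6.3: exact binomial, N = 193, null rate 0.125, expected rate 0.056, success if there are 15 or fewer events.
- P(X ≤ 15 | 0.125) = 0.0249 (stated 0.0249)
- P(X ≤ 15 | 0.056) = 0.9233 (stated 0.9233)

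Both reproduce and neither is affected by this point.

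**3. Effect on the two components.** Let f be the share of contact-evaluable subjects without an image and s the share of events that are silent, meaning found only by scheduled imaging. Neither is in the documents; both are assumed. Taking core-laboratory findings as correct, for new events in an interval:

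observed rate = true rate × (1 − f × s)

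| f | s = 0.5 | s = 1 |
|---|---|---|
| 10% | 5% lower | 10% lower |
| 20% | 10% lower | 20% lower |
| 30% | 15% lower | 30% lower |

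The factor cannot exceed 1, so within the contact-evaluable set the error goes one way only.

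**4. Effect on the composite.** The only component split available is the 30-day literature average in Protocol Appendix A, Table IV: thrombosis 2.9%, migration 1.4%, pulmonary embolism 0.2%, major bleed 1.1%, death 0.0%, total 5.6%. The imaging-dependent part is 4.3 / 5.6 = 77%. Used purely as an illustration:
- f = 10%, s = 0.5: 1.3 + 4.3 × 0.95 = 5.385%, a relative fall of 0.215 / 5.6 = 3.8%
- f = 30%, s = 1: 1.3 + 4.3 × 0.70 = 4.31%, a relative fall of 1.29 / 5.6 = 23%

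**5. The two denominators side by side (assumed counts).** With 8 confirmed events and 180 contact-evaluable subjects the rate is 8/180 = 4.44%. On imaged subjects it is 8/160 = 5.00% or 8/140 = 5.71%. If no event was missed, the last figure is too high by 180/140 − 1 = 29%.

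**6. A second effect, in the other direction.** SAP 10.3.1 keeps every subject with an event but drops event-free subjects who have no contact after the lower limit. That pushes the reported proportion up. The Kaplan-Meier estimate does not share this effect, since it keeps such subjects to last contact.

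**The case against.** Much of the information is already reported on imaged subjects. Core-laboratory occlusion enters primary patency at 12, 24 and 36 months, and movement over 1 cm enters delayed migration. The MAE line is a clinical-event view that the SAP adopts openly. Symptomatic thrombosis and migration must still be reported as adverse events (Protocol 12.2.4), phone contacts collect them, and a later image may find a silent event, though dated late. Protocol 10.10 also says the call does not replace the visit. All of this stands and limits the effect, but none of it makes an unimaged subject observed for these two components.

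Four stronger readings are tempting and are not supported:
- *The reported rates are too low.* Steps 3 and 6 pull in opposite directions for the proportion, so its net bias is not fixed.
- *Phone calls distort all time points.* The Phone Encounter exists only at 24 and 36 months. At 6 and 12 months the gap arises through a visit without an image, or an adverse-event, exit, withdrawal or lost-to-follow-up date. The SAP (version 4.0, February 2020) predates protocol version 2.0 (March 2021) and never mentions phone contacts; that they count follows from its broad definition of last contact.
- *f × s is the full detection model.* It is not. Appendix B requires venogram or IVUS for thrombosis, and neither is routinely scheduled at 6, 24 or 36 months, so a silent occlusion seen on duplex may still not qualify.
- *The 6-month migration component should be dropped.* It is prespecified, symptomatic migrations can still be found, and Appendix B accepts any imaging modality.

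An image-based rate has its own weakness: symptomatic subjects get extra imaging, so it can be too high (step 5).

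**Conclusion.** The mismatch is real. Two MAE components that only imaging can establish are given a denominator and a censoring date that need no image, although the SAP uses an imaging denominator for a closely related endpoint. Within the contact-evaluable set the component rates can be understated but not overstated. The size cannot be derived from the documents. The illustration is 5% to 30% relative for new events, assuming 10% to 30% of subjects unimaged and half to all events silent. For the composite it is about 4% to 23%, if the 30-day literature split also held later, which is a further assumption.

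Death, pulmonary embolism and bleeding are not affected. The late MAE rates are secondary and descriptive, and the post-approval primary endpoint is target lesion revascularization, so no test, alpha, power figure or success criterion changes. The point is about what the late safety rates can be taken to show.

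**What to change.** - For the thrombosis and migration components at 12, 24 and 36 months, add a rate on a denominator of the SAP 10.3.2.4 type: an evaluable core-laboratory image at or after the lower window limit, or an earlier event. For migration the image should be an X-ray or venogram.
- Add Kaplan-Meier estimates for both components censored at the last evaluable image, and use the same censoring in a sensitivity version of the MAE composite.
- Show these beside the contact-based rates, not in their place, and state the number imaged and the modality at each time point.
- Do not let a withdrawal or lost-to-follow-up date alone make a subject evaluable for these two components.
- Keep the 6-month migration component, but label it as resting on unscheduled or symptom-driven imaging, because no X-ray or venogram is scheduled then.
- Reconcile the venogram or IVUS confirmation requirement in Protocol Appendix B with a schedule at 6, 24 and 36 months in which duplex is the only routine examination of patency.

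The cost is SAP wording and programming on data already held. The downside is fewer evaluable subjects, less precise late rates and possible upward bias in the image-based line, which is why both lines are needed.
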